## 1.0 Background

Approximately \$1,400,000,000 worth of antiseptic/antibacterial mouthwash is sold in the US each year. Thus, although the exact figure is uncertain a large number of people must use such products. Antiseptic/antibacterial mouthwash use can improve oral health, by diminishing plaque and reducing gingivitis. However, such products may also have detrimental effects. In particular, prior research has demonstrated that antibacterial mouthwash can destroy the nitrate ( $\text{NO}_3^-$ )-reducing bacteria normally found in the mouth. These facultative anaerobes reduce salivary  $\text{NO}_3^-$  to nitrite ( $\text{NO}_2^-$ ), which after being swallowed and absorbed into the circulation can be further reduced by, e.g., deoxyhemoglobin, to form nitric oxide (NO). NO is a key signaling molecule involved in a variety of physiological responses, including, but not limited to, the regulation of blood flow/pressure. As a result, interruption of the bacteria-dependent enterosalivary pathway of NO production via twice-daily use of chlorhexidine-containing mouthwash (i.e., Corsodyl®) for 7 d has been shown to decrease plasma  $\text{NO}_2^-$  levels by 25% and increased systolic blood pressure by 2-3 mmHg. The latter change is potentially clinically significant, as it would raise the chance of dying of ischemic heart disease and stroke by 7 and 10%, respectively. Similar changes in plasma  $\text{NO}_2^-$  and systolic blood pressure have been found following use of cetylpyridinium-containing mouthwash (i.e., Cepacol®). It is therefore clear that chronic use of antibacterial mouthwash may have unintended negative consequences. On the other hand, use of Listerine®, an antiseptic (vs. antibacterial) mouthwash, has minimal effect on blood pressure.

In addition to influencing blood flow/pressure, NO is involved in the regulation of numerous other physiological functions, e.g., neural transmission, immune function, mitochondrial respiration, etc. This includes the regulation of muscle contractility, i.e., the force and speed of muscle contraction. Specifically, NO may (or may not) slightly suppress isometric force production, by interfering with excitation-contraction coupling at the level of  $\text{Ca}^{2+}$  release and/or by directly inhibiting actomyosin via S-nitrosylation of cysteine residues. Indirectly, however, NO causes an overall “slow-to-fast” shift characterized, in part, by increases in the rate of force development, maximal shortening velocity, and maximal power of both single muscle fibers and isolated muscles of animals. These stimulatory effects of NO are thought to be the result of activation of soluble guanylyl cyclase and thus enhanced production of cyclic GMP.

Previously, we have demonstrated that the acute ingestion of  $\text{NO}_3^-$ -rich beet juice can *increase* plasma  $\text{NO}_3^-/\text{NO}_2^-$  and breath NO and *enhance* muscle contractile function in healthy young and middle-aged individuals, athletes, and patients with heart failure. It is not known, however, whether a *reduction* in NO bioavailability resulting from use of antibacterial mouthwash can *inhibit* muscle function. Such knowledge is obviously relevant not only in the context of athletic performance but also to clinical populations (e.g., the elderly) in whom baseline muscle strength, speed, and power are impaired, thus limiting activities of daily living and increasing the risk of falls.

## 2.0 Rationale and Specific Aims

**Specific Aim #1:** To determine the effects of antibacterial mouthwash on maximal knee extensor speed and power in healthy young men and women.

We hypothesize that use of an antibacterial mouthwash will significantly reduce maximal knee extensor speed and power (primary endpoints). This will be accompanied by significant reductions in salivary  $\text{NO}_3^-/\text{NO}_2^-$  and breath NO levels (secondary endpoints).

We will test these hypotheses using isokinetic dynamometry and salivary and breath sampling in **n = 24** healthy young men and women (n = 8/group).

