## 5.0 Study Procedures

### Study Design

**Figure 1. Overall study design.**

### Study Procedures

**Study Visit 1** (Screening and muscle function testing practice): The consent statement will be reviewed with the subject including the procedures of the study and the risks of participating. Subjects will also be instructed on the requirements while in the study including not exercising on the day of study visits prior to the visit and to not attend the visit in a fasting or hungry state. They will also be asked to not consume caffeine or alcohol or use chewing gum in the 24 hours prior to the visit. They will be asked to avoid consuming foods (e.g., spinach, beets, collard greens) high in  $\text{NO}_3^-$  during this 24 hour period and to not use any other mouthwash products other than those provided during the study. Subjects who decide to participate will sign the consent and complete a screening to determine if they are eligible. If they are determined to be eligible they will then be asked to practice the muscle function test that will be used during the study that assesses the contractile function, i.e., maximal knee extensor speed and power, of the knee extensors of the subject's dominant leg. This is done using a Biodex 4 Isokinetic Dynamometer (Biodex Medical Systems, Shirley, NY).

**Study Visit 2** (Baseline Testing): participants will be asked to return and undergo baseline testing. This will include 1) collection of a saliva sample for a measurement of  $\text{NO}_3^-$  and  $\text{NO}_2^-$ , and, 2) assessment of the muscle function of the knee extensors (see Study Methods). The subjects will then be randomly assigned (via randomization.com) in four blocks of four subjects each to receive either an antibacterial mouthwash (Cepacol®, Reckitt Benckiser, Parsippany, NJ) or, as a control solution, an alcohol-free "natural" mouthwash (Tom's of Maine®, Kennebunk, ME). Participants will be asked to rinse their mouth as directed on the product's packaging for 30 s twice per day for 7 days and to record the usage of the mouthwash on a provided form. Subjects will then return for Study Visit 3. Note that although the two products differ significantly in terms of packaging, color, taste, etc., the subjects will be told that the study is simply to compare the two products, with no expectation as to the outcome.

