**Study Visit 3** (Final Testing), participants will be asked to return to undergo the same procedures as described above for Study Day 2.

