## **8.0 Statistical Considerations**

Non-PHI primary data will be stored electronically on both the measurement instruments and as Excel and/or Prism data files on the PI's university-supplied, DUO-protected laptop computer. The laptop is backed up automatically by UITS, whereas the instrument data files will be backed up manually on a monthly basis. Other data sources include the subjects' sex, age, and body mass will be collected as paper records and merged with the primary data as needed. Data quality will be assured by random auditing of single entry results and extraction/examination of data used for subsequent statistical analysis every 6 months.

Statistical analyses will be performed using Prism® version 8.0.1 (GraphPad Software, La Jolla, CA). Normality of data distribution will first be tested using the D'Agostino-Pearson omnibus test. Analysis of individual endpoints will then be conducted using a mixed model analysis of variance (ANOVA) approach, with treatment and trial number as fixed effects and subject as a random effect to account for repeated measurements. Post-hoc testing will be performed using the Šidák-Holms multiple comparison approach. A P value of <0.05 will be considered significant.

As this is a pilot experiment, we lack the preliminary data necessary to perform a formal sample size/power analysis. In previous research, however, we have observed than an *increase* in NO bioavailability resulting from ingestion of NO3-rich beet juice *increased* ( $P<0.05$ ) Vmax and Pmax by  $11.4\pm16.5$  and  $6.3\pm8.7\%$ , respectively. Assuming similar intersubject variability when NO bioavailability is *reduced* by use of an antibacterial mouthwash, our chosen sample size will allow us to detect any effect size  $\geq1.3$  with an alpha of 0.05 and 1-beta of 0.80.

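### The planned mixed model names no treatment-by-trial term, and its treatment main effect would dilute the pre/post contrast that the primary hypothesis needs

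*Combined protocol and SAP*

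**What the plan says.** Section 2.0 states one hypothesis covering two endpoints: the mouthwash "will significantly reduce maximal knee extensor speed and power (primary endpoints").

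Section 5.0 describes a parallel pre/post design. Visit 2 is an untreated baseline, after which subjects are randomised "in four blocks of four subjects each to receive either an antibacterial mouthwash" or a control product. They use it for seven days, and at Visit 3 "participants will be asked to return to undergo the same procedures as described above for Study Day 2". Section 4.0, by contrast, speaks of blinding to the order of treatment, which is crossover language.

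The analysis text in section 8.0 is short:

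- On the method: "Analysis of individual endpoints will then be conducted using a mixed model analysis of variance (ANOVA) approach".
- On the terms in the model: "with treatment and trial number as fixed effects and subject as a random effect".
- On multiplicity: "Post-hoc testing will be performed using the Šidák-Holms multiple comparison approach".
- On the threshold: "A P value of <0.05 will be considered significant".

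It lists no interaction, does not say which term or contrast gives the primary P value, and does not state sidedness. It does not define the family of comparisons that the post-hoc correction covers. No section says whether a positive result needs both primary endpoints or one.

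**The concern.** Treatment and period as fixed effects with subject random is a natural model for a crossover, where the treatment term compares products within subjects. Section 5.0 describes something else: each subject receives one product, and the first of the two analysed visits precedes any product. The effect of seven days of use is then the between-arm difference in change, which is the treatment-by-trial-number term. Treatment as a main effect compares the arms on the average of both visits, half of which cannot carry any effect of treatment.

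If the model is fitted as written, a real reduction in speed or power is likely to be missed in a trial that is already small. If the analyst adds the interaction, two candidate P values exist for each endpoint and the plan does not say which one counts. The missing success rule for the two endpoints adds a second, smaller ambiguity of the same kind.

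**Working it through.** **The plan's own figure.** Section 8.0 says that effects of 1.3 or more are detectable at alpha 0.05 and power 0.80. Four blocks of four subjects give 16, so 8 per arm. With a two-sample noncentral t (14 df), the detectable effect is 1.31 SD one-sided and 1.51 SD two-sided; power at 1.3 is 0.80 and 0.68 respectively. The figure therefore reproduces for one endpoint, one-sided, at 8 per arm. The variability it borrows is that of percentage changes in Vmax and Pmax (11.4±16.5 and 6.3±8.7%), so the statement concerns change, not the average of two visits.

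**The two candidate tests.** Let σ be the SD at one visit, ρ the correlation between Visits 2 and 3, and δ the effect of treatment, present only at Visit 3.

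- Interaction (difference in change): standardised effect δ / (σ√[2(1−ρ)]).
- Main effect (difference in the two-visit average): standardised effect (δ/2) / (σ√[(1+ρ)/2]).
- Main effect divided by interaction: √[(1−ρ)/(1+ρ)].

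In complete, balanced two-visit data these two-sample t tests are the mixed-model tests. In three simulated data sets, the random-intercept model's interaction statistic equalled the t on change (−0.6002, −1.2206, 0.2634). Its main-effect statistic without interaction equalled the t on the visit average (−0.6503, −1.9029, −1.4104).

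**Power on the main effect.** Set δ so that the interaction has 80% power at 8 per arm, two-sided 0.05 (1.507 SD of change). The documents give no ρ, so a range is assumed.

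| ρ | Ratio | Standardised effect on main effect | Power |
|---|---|---|---|
| 0.5 | 0.577 | 0.870 | 37% |
| 0.7 | 0.420 | 0.633 | 22% |
| 0.8 | 0.333 | 0.502 | 16% |
| 0.9 | 0.229 | 0.346 | 10% |

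One-sided, starting from 1.308 SD, the same ratios give about 42, 27, 21 and 14%. At ρ = 0 the ratio is 1 and nothing is lost.

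**Two primary endpoints (secondary point).** Vmax and Pmax come from one fitted curve. Their correlation r is not given, so 0 to 0.9 is assumed, with 0.95 as a check. Simulated two-sample t tests at 8 per arm, two-sided 0.05, gave:

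| r | Either suffices: false-positive chance, any difference | Both required: power when each endpoint has 80% |
|---|---|---|
| 0 | 9.7% | 64% (0.80 × 0.80) |
| 0.5 | 9.3% | 68% |
| 0.7 | 8.5% | 71% |
| 0.9 | 7.2% | 75% |
| 0.95 | 6.6% | not computed |

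If both are required, the false-positive chance is at or below the per-endpoint level. The choice of model term barely affects the either-endpoint error: at a between-visit correlation of 0.8 and r = 0 / 0.5 / 0.9, the interaction gave 9.8 / 9.3 / 7.2% and the main effect 9.8 / 9.1 / 7.1%. The model-term problem is thus one of power and of which test is meant, not of false positives.

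**The case against.** The best defence is that the interaction is implied. The section 8.0 sentence may be shorthand for a factorial repeated-measures analysis, the post-hoc step suggests that individual cells will be compared, and the detectable-effect statement is framed around change. Treatment might also be coded by the product in use at each visit, with neither in use at baseline. All of this is plausible, and it is why the documents do not show that the diluted test will be used. But the interaction is not listed, no coding is given, and post-hoc comparisons do not identify the primary test.

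A second defence is that section 4.0 implies a crossover, for which the treatment term would be appropriate. That does not fit section 5.0, which has one product per subject and one post-treatment visit. The contradiction has to be settled before any contrast is fixed.

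Third, "As this is a pilot experiment", the plan claims no formal power analysis. That lowers the stakes, but it still sets a significance threshold and quotes alpha and power.

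A reader might infer that the two primary endpoints roughly double the error rate. The documents do not support that. The hypothesis joins speed and power with *and*, which most naturally requires both; nothing says that either suffices; and the near-doubling also needs endpoints that are close to uncorrelated although they come from the same curve. Nor can the post-hoc Šidák-Holm procedure be assumed to cover the two endpoints, since its family is undefined.

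**Conclusion.** The point holds as a defect in the stated analysis model. In the parallel pre/post design of section 5.0, the treatment main effect is the wrong test of the hypothesis, and the right one is not named. At 8 per arm, two-sided, a change that would have 80% power on the interaction has about 37% down to 10% power on the main effect for between-visit correlations of 0.5 to 0.9. Those figures rest on an assumed correlation, equal variances at the two visits, complete data and the two-arm parallel reading. With missing visits the t-test equivalence is only approximate.

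The absent success rule is minor. Under the natural both-required reading there is no inflation. Under the either-endpoint reading the chance of a false positive is about 7–10% against 5% for r from 0.9 to 0, and falls towards 5% as r approaches 1. Neither gap is a design failure, and both can be repaired in the analysis text.

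**What to change.** First reconcile the order-of-treatment wording in section 4.0 with the parallel design in section 5.0, because the contrast depends on it. Then, before data are examined by arm, add to section 8.0:

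*The mixed model includes treatment, trial number and their interaction. For Vmax and for Pmax the primary test is the treatment-by-trial-number interaction, i.e. the between-arm difference in change from Visit 2 to Visit 3, tested [one- or two-]sided at 0.05.*

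The sponsor must fill in the sidedness. If two-sided, the detectable effect at 8 per arm should read about 1.5 rather than 1.3.

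Add one sentence on success. The natural reading would be: *A positive primary result requires a significant reduction in both Vmax and Pmax; no further correction is applied.* Its cost is power: about 64–75% to win on both when each endpoint has 80%, and no positive result if only one endpoint is truly affected. If either endpoint is meant to suffice, apply Holm-Šidák across the two: the smaller P value at 1 − √0.95 = 0.0253 and, only if that is significant, the other at 0.05. For the first-tested endpoint this raises the detectable effect at 8 per arm from 1.31 to 1.50 SD one-sided, or from 1.51 to 1.69 SD two-sided.

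Finally, state which comparisons the existing post-hoc correction covers. The whole change is a few sentences and needs no further data.

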## Study Methods

*Measurement of Salivary Nitrate & Nitrite:* Saliva samples will be obtained using a salivary sample collection kit (Salivette, Sarstedt, Newton, NC). The  $\text{NO}_3^-$  and  $\text{NO}_2^-$  of each sample will be determined using high performance liquid chromatography (ENO-30, Eicom USA, San Diego, CA).

*Measurement of skeletal muscle contractile functions:* A Biodex 4 System isokinetic dynamometer (Biodex Medical Systems, Shirley, NY) will be used to measure the subject's muscle contractile properties as previously described. Briefly, participants will be asked to perform three maximal isometric knee extensions with their dominant leg at a joint angle of 70 degrees. Each isometric contraction will last 5 s, with 15 s of rest in between. After 2 min of additional rest, the subject will perform three maximal isokinetic efforts at angular velocities of 1.57, 3.14, 4.71, and 6.28 rad/s, with 2 min of rest between each set. To eliminate artifacts, the dynamometer data will be "windowed" to isolate the isokinetic phase and smoothed using a nine point weighted moving average filter, after which the highest torque generated at each velocity will be multiplied by the velocity to determine the peak power at that velocity. The resulting power-velocity data will then be fit with a 2nd order polynomial function (i.e.,  $y=ax^2+bx+c$ ) which will be solved to determine the subject's maximal knee extensor velocity ( $V_{\text{max}}$ ;  $=-b/a$ ) and power ( $P_{\text{max}}$ ;  $=(4ac-b^2)/4a$ ).

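### Breath NO is a secondary endpoint with no collection step or method in the visible visits, and the section 8.0 model names no treatment-by-trial term as the test of any hypothesis

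*Combined protocol and SAP*

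**What the plan says.** Section 2.0 makes maximal knee extensor speed and power the primary endpoints. It expects reductions in salivary NO3-/NO2- "and breath NO levels (secondary endpoints") alongside them, and describes the means: "We will test these hypotheses using isokinetic dynamometry and salivary and breath sampling in" the study sample.

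Section 5.0 sets out the visits. For Visit 2: "This will include 1) collection of a saliva sample for a measurement of" NO3- and NO2-, followed by "2) assessment of the muscle function of the knee extensors (see Study Methods"). At Visit 3 participants "return to undergo the same procedures as described above for Study Day 2". Study Methods has two entries. One is saliva ("Saliva samples will be obtained using a salivary sample collection kit", then liquid chromatography) and the other is dynamometry. Mitigation of Risks adds a warm-up and blood pressure and heart rate checks around the test.

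Section 1.0 asks whether a reduction "in NO bioavailability resulting from use of antibacterial mouthwash can" inhibit muscle function. It recalls that the team's earlier work raised plasma NO3-/NO2- "and breath NO and *enhance* muscle contractile function in healthy young and middle-aged individuals".

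Section 8.0 analyses each endpoint with a mixed model. The fixed effects are treatment and trial number, and subject is random. Šidák-Holm post-hoc testing follows. No interaction is listed and no contrast is named.

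**The concern.** A named endpoint needs a step that produces its data. Staff working from the visible visit text would collect saliva, test the leg and stop. A baseline breath sample cannot be recovered once the 7-day rinse has begun, so the gap has to be closed before visits start.

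The loss has a scientific cost. Section 1.0 describes a chain: oral bacteria make nitrite, which is swallowed, absorbed and then reduced to NO. Saliva informs the first link only. The two markers that section 1.0 cites from the team's earlier work, plasma NO3-/NO2- and breath NO, have no written procedure here. If speed and power do not change, the trial will have little evidence on whether NO fell beyond the mouth.

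The second issue concerns whatever is measured. Participants are tested before and after the rinse, and each receives one product. The hypothesis is therefore about the difference between arms in change, and the terms listed in section 8.0 do not clearly estimate that. This affects the primary endpoints as much as salivary NO2-.

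**Working it through.** **Breath NO: the passages side by side**

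| Measure named in section 2.0 | Step in Visits 2 and 3 | Entry in Study Methods |
|---|---|---|
| Vmax, Pmax (primary) | yes | yes, dynamometry |
| Salivary NO3- (secondary) | yes | yes, chromatography |
| Salivary NO2- (secondary) | yes | yes, chromatography |
| Breath NO (secondary) | none visible | none visible |

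That is 1 of 3 secondary measures without a procedure, or 1 of 2 if salivary NO3-/NO2- is read as one item. The blood pressure and heart rate checks are safety measurements. They are not listed as endpoints and do not measure NO.

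**The plan's own figure.** Section 8.0 states a detectable effect size of 1.3 at alpha 0.05 and power 0.80. A two-sample t test with 8 per group and d = 1.3 gives 79.6% power one-sided and 67.7% two-sided, so the figure reproduces as a one-sided comparison. It is not an input to either part of this point.

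**What the treatment term estimates.** Let m be the baseline mean, t the shift from Visit 2 to Visit 3 in the control arm, and D the true difference between arms at Visit 3. Section 5.0 places randomisation after the Visit 2 measurements, so the expected baseline difference is zero.

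| Arm | Visit 2 | Visit 3 |
|---|---|---|
| Control | m | m + t |
| Antibacterial | m | m + t + D |

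With treatment coded as assigned arm at both visits, no interaction, and balanced complete data:

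- Treatment main effect = (m + m + t + D)/2 − (m + m + t)/2 = **D/2**.
- Treatment-by-trial interaction = [(m + t + D) − m] − [(m + t) − m] = **D**.

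For example, a Visit 3 difference of 1.3 units appears in the main effect as 1.3/2 = 0.65.

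**When the halving does not apply.** If treatment is coded as active only for the antibacterial arm at Visit 3, the treatment and trial terms reproduce all four cell means and the treatment coefficient is D. A post-hoc comparison of arms at Visit 3 also targets D. Section 8.0 specifies neither the coding nor the contrasts.

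**The case against.** **On breath NO.** The visit list is not exhaustive: the warm-up, blood pressure and heart rate appear only under Mitigation of Risks. The schema, Figure 1 and Appendix cannot be seen and may show a breath step. Section 2.0 also shows that breath sampling is intended. A reader might infer that the trial has no plan to collect breath NO; the documents do not support that. What stands is that the visible procedures contain no step, and that Study Methods, where the assay should be described, has no entry.

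**On interpretation.** A reader might infer that a null muscle result would be uninterpretable. That is too strong. An unchanged salivary NO2- would itself help to explain a null result. Aim 1 concerns the effect of mouthwash on speed and power in a self-described pilot, and promises no mechanistic test. The limit is narrower: if salivary NO2- falls and muscle does not change, nothing described shows whether NO fell downstream.

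**On the model.** A list of factors does not rule out an interaction, and the post-hoc step could hold the intended comparison. Section 4.0 also speaks of blinding to treatment order, which is crossover language. In a crossover, a treatment main effect adjusted for trial would be the natural test. It is therefore not established that the trial would test a halved effect. The omission stands, because section 5.0 describes parallel arms and nothing says which term or contrast tests the hypothesis.

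A reader might also think the model needs change in salivary NO2- as a predictor, or a mediation analysis. Neither is required: section 2.0 says only that the reductions will accompany each other.

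**Conclusion.** The point holds as a conflict over one secondary endpoint together with an under-specified model for all endpoints.

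For breath NO, the size is one named secondary measure with no data if the visible text is followed. The primary endpoints have written methods and are untouched by this part. The conclusion is limited to the visible text.

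For the model, the size is a factor of two in the quantity targeted. It rests on four conditions: assigned-arm coding at both visits, zero expected baseline difference, no interaction fitted, and balanced complete data. It concerns the main effect, not a Visit 3 contrast.

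No power loss should be quoted as the magnitude. Such figures need an assumed between-visit correlation and a scale for the 1.3. With 8 per arm, two-sided, reading 1.3 as single-visit SDs gives interaction power from 53% to above 99% over correlations of 0.3 to 0.9. Reading it as SDs of change gives 68% at every correlation. The documents settle neither, and section 8.0 gives no effect size for salivary NO2-.

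**What to change.** 1. Reconcile section 2.0 with section 5.0. Either add breath NO collection at Visits 2 and 3 and its method to Study Methods, or delete breath NO from the aim and endpoints and state that NO downstream of saliva is not measured. The first costs protocol text plus sampling that the aim already announces; the documents give no equipment or time cost. The second costs wording only. It makes the plan consistent but leaves the interpretive gap open.

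2. In section 8.0, for Vmax, Pmax and every secondary endpoint including salivary NO2-, code treatment as assigned arm and add the treatment-by-trial interaction. Name that interaction, the between-arm difference in change from Visit 2 to Visit 3, as the test of the hypothesis. State which post-hoc contrasts follow it. This costs one model term and a sentence or two. It needs no new data, because saliva and muscle function are already measured at both visits.

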### **4.0 Enrollment/Randomization**

Study participants will be given a consent form ahead of the screening visit. The study participant will be given time to review the consent form, and a study staff member will contact the potential subject to answer any questions they may have. If interested, then the potential subject will be scheduled for a meeting where the consent form will be reviewed again. The potential subject will be given as much time

as they wish to consider participation before signing the consent form and if they wish to move forward with participating, then the consent form will be signed by both the study participant and the person who reviewed the consent and obtained the participant's signature. A copy of the signed consent form will be provided to the subject. Both the participants and the investigators will be blinded to the order of treatment, which will be randomized in four blocks of four using randomization.com.

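### Section 2.0 plans 24 participants at 8 per group, but two arms and four blocks of four give 16, and the detectable effect of 1.3 cannot be checked until N, contrast and sidedness are stated

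*Combined protocol and SAP*

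**What the plan says.** **Size.** Section 2.0 gives "n = 24 healthy young men and women (n = 8/group").

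**Arms and allocation.** Section 5.0, Study Visit 2, assigns subjects "in four blocks of four subjects each to receive either an antibacterial mouthwash" or a control mouthwash. Each subject uses one product for 7 days and returns for one final visit. Section 4.0 repeats the block structure ("which will be randomized in four blocks of four using randomization.com"), but the same sentence says "Both the participants and the investigators will be blinded to the order of treatment", which is how one would describe a crossover.

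**Power.** Section 8.0 first states "As this is a pilot experiment, we lack the preliminary data necessary to perform a formal sample size/power analysis". It then cites an earlier beet juice study (changes of 11.4±16.5% in Vmax and 6.3±8.7% in Pmax). The power sentence begins "Assuming similar intersubject variability when NO bioavailability is" reduced, and concludes that "our chosen sample size will allow us to detect any effect size" of 1.3 or more at alpha 0.05 and power 0.80. The planned analysis is a "mixed model analysis of variance (ANOVA) approach, with treatment and trial number as fixed effects" and subject as a random effect. The power sentence is not tied to that model or to any contrast in it.

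**The concern.** The planned total and the length of the allocation list are basic design quantities, and here they disagree. A reader cannot tell whether recruitment should stop at 16 or at 24. If 24 is intended, the list runs out at participant 16. If 16 is intended, section 2.0 overstates the trial by half.

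The power sentence inherits the problem because it refers to the chosen sample size without naming it. The same claim can be too optimistic or too cautious, depending on which total is meant and how the effect is defined.

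**Working it through.** **1. Counts** (sections 2.0, 4.0 and 5.0)

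- Groups implied by section 2.0: 24 / 8 = 3.
- Two products at 8 per group: 2 × 8 = 16.
- Allocation list: 4 × 4 = 16.
- Shortfall if 24 is meant: 24 − 16 = 8 participants.
- 24 in two arms: 24 / 2 = 12 per arm, and 24 / 4 = 6 blocks.

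The per-group figure, the two arms and the block structure agree at 16. Only the total of 24 disagrees.

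**2. The stated detectable effect**

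Inputs from section 8.0: effect 1.3, alpha 0.05, power 0.80. Assumptions needed because the plan is silent:

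- equal allocation;
- effect size d = between-arm difference in change / SD of change;
- the test is the between-arm contrast in change, which with two visits is the treatment-by-trial interaction.

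Power comes from the noncentral t distribution with 2n − 2 degrees of freedom and noncentrality d / √(2/n), for n per arm. At n = 8 this is 1.3 / √(2/8) = 1.3 / 0.5 = 2.6. At n = 12 it is 1.3 / √(2/12) = 3.18.

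| Design | Sides | Power at 1.3 | Detectable d at 80% |
|---|---|---|---|
| 8 per arm | one | 79.6% | 1.31 |
| 8 per arm | two | 67.7% | 1.51 |
| 11 per arm | two | 82.6% | 1.26 |
| 12 per arm | two | 86.1% | 1.20 |
| Three groups of 8, pairwise, 21 df, unadjusted | two | 69.8% | 1.47 |

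The first row comes closest to the plan's figure: 8 per arm, one-sided. Under this definition, a two-sided test with 80% power at 1.3 needs 11 per arm (10 per arm gives 78.5%).

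Simulating the treatment-by-trial contrast with pre/post correlations of 0.5, 0.7 and 0.9 gave 67.6% to 67.8% at 8 per arm and 85.9% to 86.1% at 12. With the SD of change fixed, the correlation does not matter.

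**3. A different standardiser**

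If 1.3 is in units of the ordinary between-subject SD (equal at both visits), then SD of change = SD × √(2(1 − ρ)). The two-sided detectable effect at 8 per arm is 1.507 × √(2(1 − ρ)):

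- ρ = 0.3: 1.78
- ρ = 0.5: 1.51
- ρ = 0.63: 1.30
- ρ = 0.7: 1.17

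Break-even: (1.300 / 1.507)² / 2 = 0.372, so ρ = 0.628. The documents give no correlation; these values are assumed to show the range.

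**4. What the effects mean in percent**

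If the ± values in section 8.0 are SDs of percent change:

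- 1.3 SD is 1.3 × 16.5 = 21.5% in Vmax and 1.3 × 8.7 = 11.3% in Pmax;
- 1.507 SD is 24.9% and 13.1%;
- 1.197 SD is about 19.7% and 10.4%.

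The mean changes in the earlier study were 11.4% and 6.3%.

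**The case against.** The count conflict has no good answer in the visible text. Figure 1 is not shown, so a third group cannot be ruled out from it. A third group would, however, contradict section 5.0, and blocks of four do not divide equally among three arms.

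The case against the power point is stronger, and much of it stands:

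- Section 8.0 calls the trial a pilot and disclaims a formal power analysis.
- It does name an analysis model; what is missing is the link from the power sentence to a contrast in that model.
- The value 1.3 is reproduced at 8 per arm with a one-sided test, and the hypothesis in section 2.0 is directional. It can also hold two-sided in between-subject SD units if the pre/post correlation is about 0.63 or higher. So 1.3 should not be called an arithmetic error. But a directional hypothesis does not make the test one-sided, and the plan declares neither a one-sided test nor a correlation.

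Two further points are fair. If 24 is simply the mistaken number, nobody goes unallocated and the correction is one figure in section 2.0. The order-of-treatment phrase may be only loose wording for the allocation sequence, since section 5.0 gives each subject one product.

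**Conclusion.** The concern holds. The total in section 2.0 cannot be reconciled with the two arms and the 16-slot list, and this must be corrected whatever view is taken of the power statement. It rests on no assumption beyond the visible text. The agreement of 2 × 8 with 4 × 4 favours 16, but the document does not settle it.

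The power sentence is incomplete rather than shown to be wrong. If the effect is scaled by the SD of change and tested two-sided between arms, a true effect of 1.3 would be missed about 32% of the time with 16 participants (1 − 0.677) and about 14% with 24 in two arms (1 − 0.861), against the 20% stated. Other definitions change these figures, so the plan has to say which one it used.

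**What to change.** First confirm that there are two parallel arms and no third group. If so, change the reference to order of treatment in section 4.0 to treatment assignment. Then state one total consistently in sections 2.0, 4.0, 5.0 and 8.0:

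- **(a) N = 16.** 8 per arm, four blocks of four. Correct the 24 in section 2.0. Restate section 8.0 as a detectable effect of about 1.5 SD of change, two-sided alpha 0.05, power 0.80, if that is the intended definition. The cost is text only, with no extra participants or slots, but the stated figure is less favourable than 1.3.
- **(b) N = 24.** 12 per arm, six blocks of four. Extend the allocation list by two blocks (8 slots) and keep any existing assignments. Under the same definition the 1.3 statement may stand or become 1.2. The cost is 8 more participants than the present list covers, but no more than the 24 already stated, plus changes to the counts.

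In either case, name in section 8.0 the contrast (treatment-by-trial, or difference in change), its sidedness and the SD used to standardise. If 1.3 was computed one-sided, or in between-subject SD units, say so and give the assumed correlation.

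If a third group does exist, section 5.0 must describe it, the block size must be a multiple of three for equal allocation, and the detectable effect must be recomputed for the comparison of interest.
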